
2. Study aims

- Our research question is which of our current practices of covering cesarean section incisions is 1) most clinically effective at eliminating surgical site infection and 2) is most cost effective. Patient safety is paramount and we would want to use the most effective form of surgical site infection prevention bandage/covering – however we do not know which of our practice is more effective. This question is unique to both high risk patients (BMI = or > 40), which uses one type of covering versus our normal risk patients (BMI < 40).
- Our hypothesis is that a sterile silver impregnated silicone foam dressing (Mepilex Border Post-Op Ag) will be effective in maintaining a low surgical site infection rate in both high risk patients (BMI = or > 40) as well as in normal risk patients (BMI < 40). We believe using the Mepilex bandage will be a more cost effective strategy.
- Post-operative surgical site infections are uncommon in our practice (about 1%) they are clinically and financially significant complications of surgery. Strategies to minimize this known complication are essential. Our study is largely exploratory in that there aren't any adequate head-to-head studies that can help us guide our practice in selecting a wound-cover following cesarean.
- The primary clinical aim of this project is to compare and differentiate infection rates between our current two practices. The first practice that many of our OB/GYNs have selected (as part of their clinical practice, not this study) is prophylactic negative pressure wound therapy dressing (wound vac) in high risk patients (BMI = or > 40) and a standard sterile dressing in women who are normal risk (BMI < 40). This change in addition to our surgical site bundle have shown dramatic decreases in surgical site infections and many of our doctors want to continue

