- Our first of two strategies that our OB/GYNs use relies on negative pressure therapy (wound vacs) in high risk patients. We do not currently use it on obese patients (BMI > or = 30 and < 40), we do use it on patients with morbid obesity (BMI > or = 40). We use standard bandages for patients that are not morbidly obese (BMI <40), which generally is a sterile gauze. Recently our many of the OB/GYNs in our group have decided a more cost effective strategy based on high expenses from the wound vacs based on national trends with OB/GYNs as well as success in Regions Hospital with low post operative wound rates; the use the Mepilex Border Post-Op Ag dressing. The OB/GYNs who have continued with the wound-vac based strategy did not want to switch dressing types and are interested on building on our group's demonstrated improvement. In 2018 about half of our infections were in high-risk patients and half were in low-risk patients. Our infection rate is about 4-10 / 500 =

0.8-2% (annual volume is about 500 cesarean sections); we consider this to be good relative to national averages (5-10%). Our goal is 0%.

- Because post-operative infections are relatively rare the effects of bandages cannot be easily determined without a research protocol to control for confounding variables. In our goal of doing no harm our goal post-operative infection rate is 0%. We would like to systematically approach methods to help us achieve this goal.
- We use surgical site infection prevention bundles to help prevent infections including a preoperative wash, a surgical sterilization/prep, sterile technique, pre-operative antibiotics and sterile abdominal dressing. Our practices change with time and the only way to know the effect of one particular change in this overall uncommon (but clinically salient) complication is to study it; fortunately we are already practicing and collecting data in a way that studying these effects would not affect our patients.
- The negative pressure therapy costs \$300-500 per patient. A standard bandage is <\$4. A silver impregnated silicone post-op dressing costs \$20. This study would help address whether using a silver impregnated silicone foam would be cost effective in all patients or just in the high-risk population. If used universally savings in the high risk group could offset increased costs in the low risk group; costs are generally incurred by the hospital and not billed to the patient.

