- Study design will be in a prospective cohort trial. The first cohort will be patients who are having a cesarean section with OB/GYNs that prefer using paper bandages in patients with BMI <40 and prophylactic wound vacuum therapy in patients with BMI > or = 40. The second cohort will be patients who are having a cesarean section with OB/GYNs that prefer using Mepilex Border Post-Op Ag regardless of BMI.
- This will be a pilot study as infection rates are low enough that a full study would take several years. However, if difference between methods are large enough then the study would be able to reveal this (see sample size section for details)
- There will be two cohorts:

- 1) Cohort 1 - Normal risk (BMI < 40) – standard dressing (sterile gauze dressing)
High risk (BMI > or = 40) – negative pressure wound therapy / "wound vac"
- 2) Cohort 2 - Normal risk (BMI < 40) – silver impregnated silicone dressing
High risk (BMI > or = 40) – silver impregnated silicone dressing

b. Population

i. Inclusion/Exclusion Criteria [See Human Subjects items to be moved here]

- Inclusion/exclusion criteria: pregnant women who have a cesarean section; as the bandage will be applied when women are no longer pregnant (after fetus is delivered) they will technically not be pregnant at the time of inclusion in the study
- Women will be excluded from the study if their bandage / BMI are not compatible with the cohort scheme noted above (for example if the patient's OB/GYN uses a bandage that is different than a wound vac, paper bandage or Mepilex dressing).
- Specific diagnosis & procedure codes – pregnancy, cesarean section not having other abdominal surgery (example: concomitant hernia repair) except for with concomitant bilateral tubal ligation, which is often done with cesarean sections
- Specific demographic inclusion/exclusion criteria – women of child bearing age having cesarean section at Régions Hospital
- We will compare patients to a database of patients who have asked to be excluded from research, we will exclude patients who requested this. This information is kept in central HealthPartners databases.

ii. Sample size

- Sample size of records to be obtained – enrollment will be 2 years, 1000 women
- Sample size for the main analysis – anticipated follow-up of 75%, which would net 750 women

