- In the patients who have identified clinically identified infections (based on process identified above via chart abstraction) we will also obtain billing data and insurance payment information to identify the financial implications of the complications. This information will be obtained primarily by the HealthPartners Research Foundation Epic team, who will build an EMR database query to obtain this information.
- All data sources needed for the study are named (e.g., chart review, patient survey, data pull from HP electronic medical record) – all data will be abstracted from clinical EMR / Regions charts. We will also use a log from labor & delivery (all births are written down in a paper register and electronic log [MIDAS]) and compare it to our data to make sure patients are included. The Infection Prevention department also keeps a register of all post-operative infections and we will use this information that is already obtained to make sure our records are accurate (this information is readily made available to our department as it is). Additionally, billing data will be obtained for those patients in whom an infection or surgical site complication occurs to analyze complications.
- The person or job title obtaining each data source:
 - Investigators will review each chart for evidence of surgical site infection or bandage-related complications
 - The investigators in the Infection Prevention department will provide records that they already collect to the investigators to make sure data are accurate and complete
 - HealthPartners Research Institute will use Epic data queries to obtain billing and reimbursement data for patients with surgical site infections / complications. The Research Institute calls the individuals who create these queries programmers and they will work with the PI. They will also compare patients that meet inclusion criteria that have requested to not be included in research to allow us to remove those patients.

ii. Process steps for data acquisition

- All patient contact events involving data collection are described in the order they occur.
 - Patients who enter an operating room at Regions Hospital and have a cesarean section will have the cesarean section as per routine. Part of the routine, obviously, includes that the surgery will conclude and a bandage will be placed.
 - The circulator OR nurses will document the type of bandage placed, which is part of the routine already.

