- Who will be the initial contact with potential subjects: there will be no contact with the patients or physicians performing services.
- What steps will be taken to avoid coercion or undue influence in the recruitment of subjects: Bandages will be selected by the patients' OB/GYN surgeon as part of routine surgery. The patient will not experience anything different from routine care as a part of this study. When patients are admitted to the hospital we will however let them know that we are completing a study and that they may opt out of our data analysis by informing their nurse or surgeon that they wish to opt out of the data collection. Women who do not have a c-section (aka those who are excluded) will not receive this information as they are already not part of the study.
- We do not anticipate any conflicts with other studies being completed on our patient population We will request a waiver of informed consent as we are not contacting the patients, collecting additional information about patients or modifying care for these patients. We are comparing the outcomes that patients have based on their surgeon's practices.
- Who will obtain consent? We believe that a chart-review type study such as this should be exempt from obtaining consent.
- Why are we requesting a waiver?
 - Our hypothesis is that infection rates will be similar in both arms of the comparison groups and thus we believe that this study will pose minimal risk. The study itself does not impart a particular bandage on the patient but looks to see whether there are differences in outcomes over a 30-day post-operative period; thus we do not anticipate any harm. Data will be collected presented in aggregate and protected health information will not be analyzed, which also demonstrates minimal risk.
 - We believe that patients should be given the opportunity to exclude themselves from the study analysis and thus we will not include patient's that have asked HealthPartners to not be part of research.
 - Consent is obtained for non-research procedures (the surgical procedure), the surgical procedure does include having a sterile dressing. It is up to the OB/GYN surgeon to

decide on the bandage to place. This would be done by any of the nursing staff or clinical providers who see patients; this is our current practice and would not change.

How will patients be notified:

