- Possible biases include that while our study may not be powered to detect a difference, that does not inherently mean that a study does not exist if $p>0.05$. While we may draw conclusion based on this it may be a false negative. Selection bias may occur as our patient population has a tendency to be higher risk in terms of maternal morbidity than in many community hospitals. There may be ascertainment bias by the nursing staff reporting on patient complications and the obstetric team taking care of the patient in the hospital, but after the patient leaves that bias should be significantly decreased as it would take effort from the providers in the clinic to check which study group the patient is in (either accessing data or asking the patient).

5. Setting/Environment/Organizational feasibility

- The study will be conducted at Regions Hospital and otherwise by chart abstraction/review
- Cesarean section are done in the hospital-setting, thus the location is appropriate. We selected Regions Hospital as hospital leadership has already committed to using the incisional coverings despite their costs, thus the study can be completed over a long time course and over an anticipated 1000 patients. Other hospitals have not been systematically willing to use these coverings due to concern for cost; Regions pays for it due to the benefits that we believe have been demonstrated by our organization, which impacts reimbursement and thus this will be overall revenue neutral. Leadership is motivated to have the lowest overall surgical site infection. The Infection Prevention department collects much of the information we are studying and thus with minimal effort the organization will be providing much of the data abstraction.
- The study will fit in with HealthPartners Triple Aim in the following ways. It will improve the health by allowing us to study a change in our practice pattern in a systematic manner and apply the changes to our practice. This will also improve the experience of each new family as complications decrease so the time spent recovering from child birth can be focused on the new family. Finally it will help us improve our fiduciary goals by not just looking at whether infection rates are different but also if there is a significantly different cost-burden with the infections that may be conferred by the different types of incisional coverings.

6. Risks and Benefits

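### Dressing is confounded with the self-selected operating surgeon, who is recorded on no form; a significant difference could reflect surgeons and not dressings, and the plan does not say so

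*Combined protocol and SAP*

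**What the plan says.** Cohort membership follows the surgeon. Section 4.a places in cohort 1 the patients of OB/GYNs who prefer gauze below BMI 40 and a wound vac at 40 or above. For the other cohort it says: "The second cohort will be patients who are having a cesarean section with OB/GYNs that prefer using Mepilex Border Post-Op Ag regardless of BMI". Section 4.b.ii adds that about half the obstetricians use each strategy and that their volumes are similar. The surgeons sorted themselves: "The OB/GYNs who have continued with the wound-vac based strategy did not want to switch dressing types" (section 3).

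Section 3 justifies the study by saying that dressing effects "cannot be easily determined without a research protocol to control for confounding variables". Section 6 regrets that an earlier device change could not be separated from confounding.

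The three forms in 4.d hold the MRN, the cohort, BMI and a long list of patient and operative items, including skin closure, incision type, operative times, antibiotics and blood loss. None has a field for the surgeon. Section 4.e names chi-squared, t and Fisher tests and says that regression may be difficult. Section 4.f sizes a comparison of two independent samples at 431 per cohort.

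Section 4.g names limited sample size and generalizability, selection bias, ascertainment bias and a missed difference ("While we may draw conclusion based on this it may be a false negative").

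**The concern.** Each surgeon is expected to contribute to one cohort, so dressing and surgeon group cannot be told apart. Surgeons who kept the wound vac may differ from those who switched in technique, case mix or threshold for reopening a wound, and any such difference would appear as a dressing effect. This does not depend on how much individual surgeons vary within a group, and no clustering method removes it.

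Separately, if surgeons differ in infection rate, women operated on by the same surgeon are correlated, and a test that ignores this can reject too often.

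The result will be acted on. Section 8 expects practice to change within weeks of the analysis, and section 9 expects other hospitals to follow. The reader is warned of a false negative but not of a false positive.

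**Working it through.** **1. The plan's own figure.** Inputs from 4.f: 0.5% vs 3%, alpha 0.05 (taken as two-sided), power 80%. Pooled-variance formula for independent women, with mean rate 1.75%:

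n = [1.96·√(2·0.0175·0.9825) + 0.842·√(0.005·0.995 + 0.03·0.97)]² / 0.025² = (0.3635 + 0.1554)² / 0.000625 = 430.7, so 431 per cohort and 862 in total.

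This matches exactly, so 862 contains no allowance for surgeon.

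**2. How few events decide the result.** 750 women (4.b.ii) at about 1% (section 2) gives 7.5 infections, or 3.75 per cohort. With 375 per cohort, 6 vs 0 gives Fisher p = 0.031 and 8 vs 1 gives p = 0.038. This shows sparse data. It is not evidence of clustering.

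**3. Type I error of the planned tests with no dressing effect.** *Assumptions not in the documents:* 8, 12, 16 or 20 surgeons, half per strategy, near-equal volumes; gamma-distributed surgeon risks with the CV shown; 375 women per cohort. Ranges run over the number of surgeons. The no-spread row is exact; the others are simulated.

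| Rate | CV | Chi-squared | Fisher |
|---|---|---|---|
| 1% | none | 4.4% | 1.6% |
| 1% | 0.25 | 4.6-5.0% | 1.7-1.9% |
| 1% | 0.5 | 5.3-6.7% | 2.1-2.9% |
| 1% | 1.0 | 8.2-13.5% | 3.8-7.4% |
| 1.75% | 0.25-0.5 | 4.8-8.8% | 2.7-5.6% |
| 1.75% | 1.0 | 11.3-20.8% | 7.6-15.7% |

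At 3.75 expected events per cohort, Fisher is the likelier choice. At 1% it passes 5% only at CV 1.0 with 8 or 12 surgeons.

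**4. What 862 would become for an analysis that allows for clustering.** With k surgeons, DE = 1 + (N/k − 1)·ICC and ICC = p·CV²/(1 − p). At p = 1.75% and CV 0.5, ICC = 0.0175·0.25/0.9825 = 0.00445. Solving N = 862·DE gives N = 862·(1 − ICC)/(1 − 862·ICC/k): 1,650 for k = 8 and 1,062 for k = 20. At CV 0.25 the range is 904 to 978.

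**5. A surgeon-level check.** A t-test on surgeon-level infection rates, under the same assumptions, keeps type I error at about 4-6%. Its power for 0.5% vs 3% at 750 women is 61-73% with no spread and 41-64% at CV 0.5. The chi-squared test has 77.6% with no spread and 73-76% at CV 0.5.

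**The case against.** The strongest reply is that the clustering harm is small on the plan's own terms. At about 1%, Fisher stays well under 5% up to CV 0.5, and the planned tests lose only a few points of power. One hospital with a shared prevention bundle suggests little spread between surgeons. The plan is also candid about its status: "This will be a pilot study as infection rates are low enough" (4.a) and "Our study is largely exploratory in that" (section 2). Several operative variables that vary by surgeon are collected, and the surgeon can be recovered through the MRN until identifiers are destroyed on publication (section 7).

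Most of this stands as regards clustering. A reader might infer that the patient-level test overstates certainty whenever surgeons differ; for Fisher at 1% the figures do not support that. A reader might also infer that 4.g warns only of a missed difference, but it names selection and ascertainment bias too, although neither concerns the surgeon.

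The reply does not meet the confounding. Conservatism of Fisher's test does nothing against a systematic difference between two self-selected groups, 4.e commits to no adjustment for the operative variables, and the homogeneity claimed in 4.g cannot be checked without a surgeon field. Exploratory status calls for caution in reading a result, but the plan states that caution in one direction only.

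It is also fair that a surgeon-level test could reassure falsely, since a difference between surgeon groups would pass it. The fix has to say so.

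**Conclusion.** The concern holds and should be fixed. Dressing is confounded with self-selected surgeon, the surgeon goes unrecorded, and the limitations omit both this and the possibility of a false positive. That part rests on the documents alone.

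The clustering part is conditional. Under the assumed 8 to 20 surgeons it is nil to small at a 1% rate up to CV 0.5, and material only with large spread: at CV 1.0, up to 13.5% (chi-squared) or 7.4% (Fisher) at 1%, and up to about 21% or 16% at 1.75%. The documents do not say where in this range the practice lies. They therefore do not support a claim that the planned test is invalid, or that a significant result would be wrong.

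**What to change.** 1. **Second form (4.d).** Add a coded surgeon ID, taken from the chart through the MRN before identifiers are destroyed. Keep it off the third form so that the blinding of the analyst is preserved. Report the number of surgeons and the infections per surgeon.
2. **Section 4.e.** Pre-specify one sensitivity analysis beside the patient-level test: a t-test on surgeon-level infection rates. Replace it with a cluster-robust interval with small-sample correction only if a surgeon has patients in both cohorts. That could happen, because the dressing is recorded woman by woman ("The circulator OR nurses will document the type of bandage placed", 4.c.ii). Naming one method avoids a choice made after seeing the data.
3. **Section 4.f.** State that 862 and 80% power assume no between-surgeon variation.
4. **Section 4.g.** State that dressing is confounded with self-selected surgeon, that agreement between the two tests does not rule this out, and that a significant result could be a false positive.

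**Cost.** One column and a few sentences. The field comes from the chart, so the commitment that "there will be no contact with the patients or physicians performing services" is kept. The document is dated 6/12/2019 and abstraction starts 7/1/2019 (section 8), so on that timeline the field can be in place before any chart is abstracted. The downside is the lower power of the sensitivity test, even when surgeons do not differ, so 4.e should say that its non-significance alone does not overturn the patient-level result.

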- A rationale for selecting the sample size is provided and is summarized as due to a 0.5-3% post-operative infection rate in order to adequately power a study to find a difference – the records to be obtained would include all patient who satisfy the inclusion criteria, approximately 500 per year. Based on this study population and anticipated surgical site infection rate of 0.5% in best case scenario and 3% (both better than the national mean) with a power of 80% and alpha 0.05 we would need a study size of 862. As this is the first study of its kind in the comparison groups it would be clinically salient to find significance or not find it as both results would be clinically helpful in guiding obstetricians.
- Follow-up in the postpartum period is notoriously low, approximately 50%. After cesarean most women tend to at least follow-up for an incision check in the clinics or go to the emergency room and thus it would be reasonable to expect 75% follow-up based on author prior clinical experience.
- Counts of patients expected to be study-eligible are approximately 500 / year based on our standard variation in annual cesarean rates.
- Our two cohorts should be of similar size. Approximately half of the OB's have chosen each closure method as their method of choice. All surgeons have similar obstetric volume and so the total group sizes will likely be similar in size. There are no anticipated changes to the current practice over the next two years.

c. Data collection process

i. Process steps for identification of patients or records

- We will use obstetric logs (paper log), MIDAS (electronic log) and hospital/clinic EMR to identify any women who have a cesarean section at Regions hospital in the date window of interest.
- The PI and co-investigators will review the patient records in the bullet points above for surgical site infection. Currently the Infection Prevention department already does this; the charts of the patients identified will be abstracted. All patients in the study will have their charts abstracted as

well by the PI for suggestion of surgical site infection or for any potential complications related to the surgical site coverings (standard gauze bandage, silver impregnated silicone dressing or negative pressure wound therapy device). Any question will be reviewed by an additional co-investigator obstetrician; if there is a discrepancy then the third co-investigator will make a final determination.

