Descriptive statistics generally as mean or total; chi-squared, Students t-test, Fisher exact tests as appropriate. Regression may be difficult with low infection rates.

- Anticipate roughly 300-600 participants per cohort (after accounting for patient follow-up)
- Variables per section "E" above
- Silver impregnated silicone dressing versus wound vac/paper dressing will be 1 study analysis. Then stratification by arm will be completed
- Infection rate will be reported as number (proportion). Clinical significance will be $P<0.05$. Dichotomous/categorical data will be reported as a proportion. Continuous variables may be dichotomized versus kept as a scale depending on the analysis (for example in our $BMI > or = 40$ versus $BMI <40$ would be one example of dichotomized data). Hemoglobin a1c (a measure of diabetic control) would likely be dichotomized into <7 (preferred in pregnancy) versus >7 .
- Missing data will be analyzed on a per-participant basis—for example if there is a recent BMI and not one done the day of surgery that may be used. Missing data that is used will be reviewed by a second investigator for appropriateness, if not certain then a third investigator will opine as to the appropriateness as a tie-breaker.
- We will obtain hospital / practice billing data averages (for patient care in general) to multiply by the additional visits (ER, home healthcare or clinic), admissions, procedures and surgeries to increase the clinical salience of our analysis.
- [name] wrote the analysis plan and will complete the analysis plan. SPSS v25 or similar will be used. A statistician from the HealthPartners Institute Research Methodology Group will be used for post hoc analysis for additional insight. [name] is confident he can complete descriptive as well as analytic statistics based on prior studies. He has generally performed his own statistical analysis when performing original research; post hoc statistician analysis has been consistent with his findings in these studies.

f. Power analysis or statement of precision

The following study parameters were used to find an appropriate sample size:

Study Parameters:

Incidence, group 1:	0.5%
Incidence, group 2:	3%
Alpha:	0.05
Beta:	0.2
Power:	0.8

The following sample sizes would be needed to have adequate power with a dichotomous endpoint, two independent sample study:

Sample Size:

Cohort 1	431 (silver impregnated silicone bandage)

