Cohort 2	431 (negative pressure therapy, sterile gauze bandage – composite)
Total	862

The study might be underpowered to demonstrate the hypothesis when comparing the cohorts. Unlike certain interventions a positive or negative difference would be clinically salient as the groups have significantly different costs. Thus regardless of outcome this study could help our group modify practice.

g. Strengths and limitations

A strength of the study is the relatively homogenous environment in which the study will be conducted. While this also would decrease applicability to the general field of obstetrics it increases power to find differences where they might be too difficult to find otherwise. This includes a single hospital with a group of obstetricians that are all willing to participate in conducting this study (based on administrative meetings where we committed to studying a change in our practice prior to completely implementing it). Additional strengths include that this will be the largest trial of its kind and rather than studying an intervention against an outdated method we are comparing three specific interventions in a head-to-head trial (in two cohorts). An additional strength of this study is that our Infection Prevention co-investigators already collect much of the information in this study and have a robust system to detect surgical site infections that are noted outside of our system. A final benefit of this study is that it is able to incorporate two state-of-the-art interventions already being done that are low-risk and demonstrate which has the lowest complication rate to help inform our practice and the field of obstetrics in clinical care. In adding cost data to this analysis we will also help providers and hospitals maintain their fiduciary duties.

- Limitations are primarily related to our sample size; unfortunately it is not possible in our practice to increase enrollment numbers without extending the study by several years; while this could be done it would not anticipated. Another limitation (despite being a strength) is that our practice is rather homogenous and so generalizability to other practices may be limited; as this would be the only data of its kind, this should at least help spur further research.

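### The only stated power (80%, for 862 women) belongs to a larger sample than the 750 the plan expects to analyse; at 750 it is about 74%

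*Combined protocol and SAP*

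**What the plan says.** - **4.b.ii, expected size.** Records will be obtained for 1,000 women over two years, with "anticipated follow-up of 75%, which would net 750 women" for the main analysis.
- **4.b.ii, required size.** For rates of 0.5% and 3%, "with a power of 80% and alpha 0.05 we would need a study size of 862". Section 4.f repeats this as 431 per cohort.
- **4.b.ii, balance.** "Our two cohorts should be of similar size".
- **4.a.** The study is called a pilot, but "if difference between methods are large enough then the study would be able to reveal this (see sample size section for details").
- **4.e.** "Anticipate roughly 300-600 participants per cohort (after accounting for patient follow-up"). The tests listed are "chi-squared, Students t-test, Fisher exact tests as appropriate", with no rule for choosing between chi-squared and Fisher.
- **4.f and 4.g, caveats.** "The study might be underpowered to demonstrate the hypothesis when comparing the cohorts". Sample size is named as the main limitation, and "it is not possible in our practice to increase enrollment numbers without extending the study by several years". Section 4.g adds that a non-significant result may be a false negative.

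No section gives power or a detectable difference for 750 women.

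**The concern.** Two sample sizes stand in one subsection, and the only power figure is attached to the one the plan does not expect to reach. Section 4.a sends the reader to the sample size section to learn how large a difference the study could reveal, and the only contrast found there belongs to 862.

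This matters because the plan means to use a null result. Section 6 says that if no clinical difference is seen, the practice can take cost into account. Section 4.b.ii says that finding or not finding significance would both guide obstetricians. Section 8 foresees practice change within weeks of the analysis. A reader weighing a null result needs the power of the study that was planned. The plan itself faults the earlier randomised trial (section 3) for being underpowered, citing its final pool of about 160 rather than the 300 in the study. The same standard applies here.

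**Working it through.** **Inputs.** Rates 0.5% and 3%, alpha 0.05, power 80% (4.b.ii, 4.f); 1,000 records, 75% follow-up, 750 analysed (4.b.ii); cohorts of similar size (4.b.ii), taken as 375 each. The plan does not state sidedness. Two-sided is inferred because the two-sided pooled formula without continuity correction gives exactly 431; the one-sided version gives 340 and the continuity-corrected two-sided version 508.

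**1. Reproduce the plan's figure.**

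n per cohort = [1.960·√(2p̄(1−p̄)) + 0.8416·√(p₁(1−p₁)+p₂(1−p₂))]² / (p₂−p₁)², with p̄ = 0.0175.

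- √(2 × 0.0175 × 0.9825) = 0.18544
- √(0.005 × 0.995 + 0.03 × 0.97) = 0.18459
- n = (1.960 × 0.18544 + 0.8416 × 0.18459)² / 0.025² = 430.7, so 431 per cohort and 862 in total

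This matches the plan. There is no term for loss to follow-up, so 862 must be compared with 750, not with 1,000.

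**2. The gap.**

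- 862 − 750 = 112 women, and 112/862 = 13%
- Follow-up needed to reach 862 from 1,000 records: 862/1,000 = 86.2%
- Records needed at 75% follow-up: 862/0.75 = 1,149.3, so about 1,150

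**3. Power at 375 per cohort, same formula.**

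z = (0.025 × √375 − 1.960 × 0.18544) / 0.18459 = 0.654, so power = Φ(0.654) = 74.3%.

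**4. Power for the tests named in 4.e**, by enumerating all binomial outcomes with equal cohorts and independent women:

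| True rates | Per cohort | Formula | Fisher exact | Uncorrected chi-squared |
|---|---|---|---|---|
| 0.5% vs 3% | 431 | 80.0% | 77.4% | 83.8% |
| 0.5% vs 3% | 375 | 74.3% | 69.5% | 77.6% |
| 0.5% vs 2% | 375 | 45.6% | 33.0% | 44.4% |
| 0.8% vs 2% | 375 | 28.7% | 18.4% | 26.1% |

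Within each method, going from 431 to 375 costs 5.7, 7.9 and 6.2 points at the design contrast. If chi-squared is used when the smallest expected count is at least 5 and Fisher otherwise (an assumed rule), power at 375 is 75.5%.

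The last two rows are illustrations. The 0.8% and 2% are the ends of the service-wide range in section 3, used here as if they were cohort rates; the plan does not plan on either contrast.

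**5. Detectable difference at 375 per cohort.** For 80% power against 0.5%, the other rate must be about 3.28% (formula), 3.40% (Fisher) or 3.10% (chi-squared).

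**6. The cohort range in 4.e.** With about 750 analysed, 600 in one cohort leaves 750 − 600 = 150 in the other, below the range's own floor of 300. With 600 in both, the total of 1,200 exceeds the 1,000 records. The lower end can hold: 300 and 450 sum to 750.

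**The case against.** The strongest reply is that the weakness is largely disclosed. The study is called a pilot, says it might be underpowered, names sample size as its main limitation, explains why it cannot enrol more, and warns of a false negative. The figures 1,000, 750 and 862 are all in 4.b.ii, so an attentive reader can see the shortfall. The loss at the design contrast is also no larger than the 8-point spread between the two candidate tests at 375 per cohort.

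This supports treating the point as a reporting gap of moderate weight. It does not close it, because the caveats carry no number and are never tied to the 750.

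Three narrower objections stand in part:

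- **The low figures for smaller differences are mostly not due to the shortfall.** At the full 431 per cohort the formula gives only about 51% for 0.5% vs 2% and 32% for 0.8% vs 2%, so going to 375 costs about 5 and 4 points. They show what the study can detect and should not be read as the size of the 862-versus-750 gap. Any such scenario put into the protocol should be labelled illustrative.
- **Cohort balance is uncertain.** The plan promises only similar sizes. A 300/450 split gives 69.3% or 75.7% by the formula, depending on which cohort is larger, so about 375 is an expectation and not a guarantee.
- **Independence is assumed.** Dressing follows surgeon preference, so the figures look more precise than the design supports.

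**Conclusion.** The concern holds. Neither calculation is wrong; they are unreconciled, and the stated 80% does not apply to the analysis set the plan expects. At 750 women the power for 0.5% vs 3% is about 74% by the plan's own formula, and 69.5% to 77.6% depending on the test. If those were the true rates, the study would miss the difference about 26% of the time (22.4% to 30.5% by test), against the 20% implied by the stated power. That is the miss rate at one assumed difference, not the probability that a null result is false.

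The figures assume a two-sided 0.05 test, equal cohorts, independent women and 75% follow-up. The shortfall alone is modest, and it should be corrected because the plan intends to act on a null result.

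**What to change.** In 4.b.ii and 4.f, add:

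> The figure of 862 is the number analysed. The expected 750 analysed women (375 per cohort) give about 74% power for 0.5% vs 3% (exact: Fisher 69.5%, uncorrected chi-squared 77.6%). For illustration, power is about 46% for 0.5% vs 2% (33%, 44%) and about 29% for 0.8% vs 2% (18%, 26%). Power of 80% needs about 0.5% vs 3.3% (3.4%, 3.1%). These figures assume a two-sided 0.05 test, equal cohorts and independent women.

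If a shorter text is preferred, the 0.5% vs 3% figures and the detectable difference are the essential part.

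In 4.e, replace the 300 to 600 range with about 375 per cohort (about 750 in total). If a range is kept to allow for imbalance, its two ends should sum to about 750.

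If 4.g uses power to discuss a null result, add that at true rates of 0.5% and 3% the study would miss the difference about 26% of the time.

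The cost is text only, with no added enrolment, chart review or analysis. The stated power becomes less favourable, about 74% in place of 80%.
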